Clinical Study Protocol

SPIROMIND-STUDY

A pilot randomized controlled trial to examine the feasibility and effects of a brief digital mindfulness-based intervention for stable COPD patients

Version 2.0 / 026.04.21

Confidentiality Statement

The information contained in this document is the property of the sponsor of this study. It is therefore provided to you in confidence. It is understood that this information will not be disclosed to others without written authorization.

EXECUTIVE SUMMARY

Background: COPD patients frequently experience psychological distress (symptoms of anxiety and depression) as well as psychophysiological symptoms of stress. So far, pharmacological treatments showed only limited effectiveness. Therefore, a need for further treatment options emerges, which was also reported by COPD patients themselves. MBIs were shown to be effective in older and chronically ill populations and appear attractive to stable COPD patients. Hence, the presented study will follow this idea and investigate an app-based mindfulness intervention using ecological momentary assessment (EMA) and psychophysiological measures. This study's primary research objective is to examine a) whether a brief digital mindfulness-based intervention is feasible for stable COPD patients. and b) whether a brief digital mindfulness-based intervention can reduce psychological distress in stable COPD patients. Additionally, this study aims to investigate immediate effects of mindfulness exercises as well as intermediate and long-term effects on other respiratory, psychophysiological and psychological variables.

Methods: This pilot randomized controlled trial intends to include 30 stable COPD patients, who are psychologically distressed and will be randomly assigned to the intervention (appbased mindfulness + treatment as usual) and waitlist control (treatment as usual) condition. The intervention group will be introduced to the intervention in a face-to-face learning phase (single day) conducted by the study coordinator while being hospitalized. Patients in the intervention group will be instructed to practice mindfulness daily using at least one of 4 short exercises (10-15 minutes) over a period of 8 weeks, starting in the hospital and continuing at home. The exercises will be delivered by a software (movisensXS). Additionally, dyspnoea, stress, relaxation, affect and oxygen saturation (assessed by a pulse oximeter) will be assessed before and after each exercise via the software.

Questionnaire data will be collected equally in both groups at 5 measurements: baseline, after 4 weeks, after the intervention (8 weeks) and at follow-up (4 and 6 months). Physiological measures (heart rate variability, electrodermal activity, heart rate) will be conducted at the same 5 measurements, using an ecg and eda sensor (movisens EcgMove4, movisens EdaMove4). Physiological measures will be assessed during the conduction of a cognitive stress test (Stroop-test), as well as before and after the conduction (at rest). Hair cortisol will be collected at baseline, after the intervention (8 weeks) and at follow-up (4 and 6 months). Face-to-face exit interviews will be conducted in the intervention group after 8 weeks to further assess patients' experiences with the intervention.

The primary outcome measures are psychological distress and the intervention's feasibility. The secondary outcome parameters for immediate effects of mindfulness exercises will be dyspnoea, stress, relaxation, affect (anxiety, depression, happiness) and oxygen saturation. The secondary outcome parameters for intermediate and long-term effects are heart rate variability, electrodermal activity, heart rate, health-related quality of life, health status impairment, fatigue, breathlessness catastrophizing, perceived and chronic stress, mindfulness and self-compassion. Additionally, compliance regarding medication-intake, perception of exacerbations, frequency and intensity of exacerbations and hospitalization rate as well as patients' experiences with the intervention are assessed.

Klinik Ottakring

Analysis: This study will realize a mixed methods analysis. Differences between conditions as well as moderating and mediating effects will be calculated. The intermediate pre-post effects of mindfulness exercises will be analysed using multi-level analyses (HLM). Interview data will be analysed using thematic analysis.

Klinik Floridsdorf

Fakultät für Psychologie

Discussion: The study aims to assess the feasibility of a brief app-based mindfulness intervention for stable COPD patients who are psychologically distressed and intends to investigate its effects on psychological distress and various other psychological, psychophysiological and respiratory variables. The results of this study could serve as basis for following large-scale RCTs and advance the future implementation of app-based MBIs as add-on treatment in the clinical practice.

Ethics: The study will be conducted in accordance with the Declaration of Helsinki. It will be asked for examination and agreement by the ethics committee of the city of Vienna. Ethics approval for a similar study for COPD patients following acute exacerbations has already been obtained by the ethics committee of the city of Vienna (serial number EK 20-177-VK).

SPONSOR, INVESTIGATOR, MONITOR AND SIGNATURES

Klinik Floridsdorf

Sponsor/or representative (OEL) (AMG §§ 2a, 31, 32)

Karl-Landsteiner-Institut für Lungenforschung und Pneumologische Onkologie

Signature (OEL)

Investigators (AMG §§ 2a, 35, 36)

Prim. Priv.-Doz. [name], Klinik Ottakring, Vienna, Austria (principal investigator)

Signature

Univ.-[name]. [name], Department of Clinical and Health Psychology, University of Vienna, Austria

Signature

[name], Klinik Ottakring, Vienna, Austria

Signature

[name], B.Sc., Department of Clinical and Health Psychology, University of Vienna, Austria (study coordinator)

Signature

Date

Date

Date

Fakultät für Psychologi

Date

Date

Klinik Floridsdorf

Monitor/ or Representative of CRO (AMG §§ 2a, 33, 34)

Medizinische Universität Wien KKS - Koordinationszentrum für Klinische Studien [name]

Signature

Date

Clinical Trials Centres:

2.Medizinische Abteilung mit Pneumologie, Klinik Ottakring, Vienna, Austria Abteilung für Innere Medizin und Pneumologie, Klinik Floridsdorf, Vienna, Austria

Associated Departments:

Department of Clinical and Health Psychology, University of Vienna, Austria

Wiener Gesundheitsverbund Klinik Floridsdorf

Fü

CLINICAL STUDY PROTOCOL

TITLE	A pilot randomized controlled trial to examine the feasibility and effects of a brief digital mindfulness-based intervention for stable COPD patients
BACKGROUND	BACKGROUND: Multiple reviews showed that symptoms of anxiety and depression (=psychological distress) are significantly more prevalent in COPD patients than in the general population (Matte et al., 2016; Willgoss & Yohannes, 2013). Both correlate with a decrease in health-related quality of life (e.g. Blakemore et al., 2014), but are also associated with other worsened health outcomes, such as a poorer functional status, higher mortality rates and more frequent and longer hospitalisations (e.g. Atlantis, Fahey, Cochrane, & Smith, 2013; Panagioti, Scott, Blakemore, & Coventry, 2014; Pumar et al., 2014). Moreover, breathing problems have been identified as major stressor for COPD patients (Andenæs, Kalfoss, and Wahl, 2006). If stressful events like dyspnoea are experienced frequently, this might determine a maladaptive activation of the bodily stress systems, meaning the autonomous nervous system (ANS) and the hypothalamic-pituitary-adrenal axis (HPA axis), leading to an ongoing dysregulation of these systems and resulting in chronic stress (e.g. Chrousos, 2009). Studies have shown a general sympathetic overactivity of the ANS in COPD patients (Van Gestel, Kohler, & Clarenbach, 2012). Furthermore, COPD is characterized by a systemic inflammatory response manifesting with increased inflammatory cytokines (Singh et al., 2018). As the inflammatory response is regulated by both the ANS as well as the HPA axis (Glaser & Kiecolt-Glaser, 2005), this adds up to the evidence of an ongoing dysregulation of these stress systems in COPD. Such dysregulations, in turn, are known to increase the risk for mental and physical health problems (e.g. Adam et al., 2017). Therefore, it seems crucial to address both, psychological distress and stress, in mental health interventions for
	COPD patients. In addition, high-quality evidence regarding the effectiveness of pharmacological interventions in reducing symptoms of anxiety and depression in COPD is limited (Cafarella, Effing, Barton, Ahmed, & Frith, 2013), with psychological interventions showing greater treatment efficacy when compared to pharmacotherapy (Usmani, Chahhoud, Esterman, & Smith, 2018). Hence, further psychosocial treatment approaches focusing on the reduction of psychological distress as well as psychophysiological stress responses and dyspnea should be investigated. The results of a recent study conducted by our team underline this necessity, as hospitalized COPD patients reported the need for further treatment options. In our previous study, we were able to show that most hospitalized COPD patients (14/20) would be interested in participating in a mindfulness-based intervention (MBI). Mindfulness is a promising option in the treatment of COPD patients, as it significantly reduced symptoms of stress (psychological and physiological parameters), anxiety and depression in previous studies (Cillessen, Johannsen, Speckens, & Zachariae, 2019; Pascoe, Thompson, Jenkins, & Ski, 2017). Furthermore, mindfulness was beneficial for older adults (Hazlett-Stevens, Singer, & Chong, 2019) and patients with other chronic conditions (Bohlmeijer, Prenger, Taal, & Cuijpers, 2010). Despite the above, the existing evidence on MBIs for COPD patients is very scarce. So far, only eight primary studies examined the effects of MBIs on COPD patients (e.g. Chan, Giardino, & Llarson, 2015). Two of them investigated brief MBIs

in COPD inpatients (Perkins-Porras et al., 2018; Tan et al., 2019). To summarize the few results, MBIs appeared to be feasible and attractive to COPD patients and showed a trend for being effective in the improvement of anxiety and depression symptoms (Farver-Vestergaard, O'Toole, et al., 2018) and dyspnea (Tan et al., 2019). Perceived or psychophysiological stress responses have been considered in only two studies, which found no effects on perceived stress and inflammatory stress markers (Farver-Vestergaard, O'Toole, et al., 2018; Mularski et al., 2009). Only one study investigated a digital MBI (Farver-Vestergaard, O'Connor, et al., 2018), which had very high attendance rates but found only trends in improvement of psychological distress. However, digital interventions seem to be especially promising for COPD patients, as they are often limited in their mobility and therefore seek for interventions feasible for the conduction at home. Moreover, digital health applications have become of particular interest and importance since the onset of the ongoing Covid19-pandemic. To summarize, well-designed, high quality studies are needed to confirm the beneficial effects of MBIs on psychological distress and dyspnea, but also to further investigate the effects on perceived and psychophysiological stress. This is crucial to enable an evidence-based use of MBIs in clinical settings.
PRESENT STUDY:
The presented pilot and feasibility randomized controlled trial will investigate a mindfulness-based ecological momentary intervention (EMI) applicable in the daily life of COPD patients. The intervention is adapted to patients' needs and limitations, which were assessed in our previous study and were found to be crucial for patients' adherence. This will be the first study to examine an app-based mindfulness EMI for COPD patients.
The study will use an ecological momentary assessment (EMA) design, which allows real-time measures in the patients' daily life. Previous research showed EMA
to be more valid and sensitive in investigating dynamic psychological aspects (e.g. affective variables). Moreover, it was able to detect therapeutic effects earlier and minimized retrospective biases compared to standard questionnaire assessments (Ebner-Priemer & Trull, 2009).
The delivery via an app was chosen to improve adherence and to suit patients' difficulties regarding mobility. Additionally, this allows to provide a personalized
intervention, as different exercises can be chosen based on patients' preferences and needs. Furthermore, mobile health is an emerging and promising field, which
is both economic and feasible when used in health care. In addition, as personalized medicine is a growing field of interest and holds great potential, the presented study aims to identify treatable traits and patients who benefit most from the intervention.
Finally, this study will examine the effects of mindfulness on

Finally, this study will examine the effects of mindfulness on psychophysiological stress markers (e.g. heart rate variability), which play an important role in COPD (Andreas, Haarmann, Klarner, Hasenfuß, & Raupach, 2014). It is well known that physiological and psychological stress symptoms can be reduced by MBIs (Pascoe et al., 2017). Yet, this effect has poorly been studied in COPD patients to date.

OBJECTIVES	Primary Research Questions
	• Is a brief digital mindfulness-based intervention feasible for stable COPD patients?

Klinik Ottakring

Klinik Floridsdorf

V

Wiener Gesundheitsverbund Klinik Floridsdorf

	• Can a brief digital mindfulness-based intervention reduce psychological distress in stable, but psychologically distressed, COPD patients (using the "Hospital Anxiety and Depression Scale")?
	Secondary Research Questions
	• What are the immediate effects of a short mindfulness exercise for stable COPD patients on dyspnea, acute perceived stress, relaxation, affect and oxygen saturation?
	• What are the effects of daily short mindfulness practice for stable COPD patients on patients' stress level and stress reactivity (heart rate variability, electrodermal activity), when being exposed to a cognitive stressor (Strooptest)?
	• What are the effects of daily short mindfulness practice for stable COPD patients on patients' dealing with the exposure to a cognitive stressor (Stroop-Test)? Are there effects on anxiety, panic, acute perceived stress, relaxation, affect and oxygen saturation?
	• What are the intermediate and long-term effects of daily short mindfulness practice for stable COPD patients on health-related quality of life, health status impairment, fatigue, breathlessness catastrophizing, perceived stress, mindfulness and self-compassion?
	 Does the compliance regarding medication differ between the groups due to the intervention?
	How do patients experience the intervention?
	 How often do patients meditate by using the app? How long? When? Do they prefer a specific mindfulness exercise?
	• Which patients benefit the most from the intervention (moderating factors, e.g.
	 age)? Do mindfulness and self-compassion mediate the intermediate and long-term effects on psychological distress?
DESIGN / PHASE	 pilot and feasibility study randomized controlled trial including follow-up
	• two treatment arms: intervention + treatment as usual (TAU) vs. waitlist (TAU)
	 ecological momentary assessment (EMA) study ecological momentary intervention (EMI) study (app-based)
	 prospective and experimental
	mixed methods analysismulti-centred
	multi-centred
STUDY PLANNED DURATION	6 months (8 weeks intervention + follow-up)
CENTER(S)/	Respiratory unit of the "Klinik Ottakring", Vienna, Austria
COUNTRY(IES)	Respiratory unit of the "Klinik Floridsdorf", Vienna, Austria
PATIENTS /	Groups:
GROUPS	 Intervention group: mindfulness exercises + TAU Waitlist control group: TAU
	Sample size: 30 COPD patients (15 patients in each group)
L	

V

Wiener Gesundheitsverbund Klinik Floridsdorf

	Sampling method: screening of all eligible patients during survey period, inclusion of all eligible interested patients
	Blinding: single blinding (of assessors)
	Allocation: equal treatment allocation via block randomization
ETHICS	 patients' written informed consent pseudonymisation of patients: Patients' personal data is noted on 2 documents: the patients' information (name, birth date, code) and the patients' contact details (name, birth date, address, phone number, email address, code). These documents are safely stored in a locked cupboard in the Klinik Ottakring, Vienna, Austria. Only members of the research team have access to the cupboard's key. After the screening, the patient is given a unique reference code (continuous numerical code starting from 01). In the following, only this numerical code will be used to allocate the data to the patient. The allocation of the patients' personal data to their numerical code will only be possible using either the patients' information or the patients' contact details. pseudonymised data analysis provision of mindfulness intervention to waitlist control group after study completion examination and agreement by the ethics committee of the "Wiener Krankenanstaltenverbund", Vienna, Austria
INCLUSION CRITERIA	 spirometry confirmed (FEV1 <80%) COPD diagnosis psychological distress (as assessed by the Hospital Anxiety and Depression Scale): HADS-A ≥ 8 OR HADS-D ≥ 8 OR HADS total score ≥ 16 age ≥ 40 years ability to understand German physical and mental capability to attend the intervention, judged by the treating physician life expectancy > 6 months as judged by treating physician ability to use a smartphone
EXCLUSION CRITERIA	 ability to use a smartphone auditory impairment active asthma diagnosis any other known severe comorbidities such as heart failure (LVF<35%), uncontrolled diabetes, concomitant cancer, stroke, unstable coronary heart disease, respiratory failure history of/current severe psychological disorder (e.g. schizophrenia, severe cognitive impairment) current acute exacerbation of COPD any other relevant acute health crisis interfering with the study intervention (e.g. Covid-19) receiving any psychosocial treatment (e.g. psychotherapy) regular other systematic mind-body-practice
STUDY PERIODS	Period 1: individual mindfulness practice at home (baseline - 8 weeks)
	Period 2: Follow-up (3 months and 6 months)

VV

Wiener Gesundheitsverbund Klinik Floridsdorf

MEASUREMENTS	Paper-pencil data collection (baseline, 4 weeks, 8 weeks, 4 months, 6 months) psychological distress, perceived stress, health related quality of life, health status impairment, fatigue, mindfulness, self-compassion, breathlessness catastrophizing
	Psychophysiological data collection (baseline, 4 weeks, 8 weeks, 4 months, 6 months): heart rate variability, electrodermal activity (before, during and after the conduction of a cognitive task (Stroop-test))
	EMA data collection (daily for intervention period of 8 weeks):
	 pre-meditation (event-based): dyspnea, acute perceived stress, relaxation anxiety, depression, happiness, oxygen saturation (pulse oximeter) post-meditation (event-based): dyspnea, acute perceived stress, relaxation anxiety, depression, happiness, oxygen saturation (pulse oximeter)
STUDY TIME-LINE	Recruitment:
	 pulmonary ambulances of the Klinik Ottakring and Klinik Floridsdorf previously hospitalized COPD patients in the Klinik Ottakring and Klinil Floridsdorf invitation to the intervention via telephone call or personal invitation in the pulmonary ambulance (flyer and oral information)
	• invitation to the intervention via posting a flyer on social media (Facebook)
	Telephone-Screening:
	screening for inclusion and exclusion criteria
	Period 1 (patients' home)
	 Day 0: Informed consent Baseline data collection Sociodemographic and medical data Paper-pencil data collection Chronic stress (collection of hair sample) Psychophysiological data collection
	Day 1:
	 Introductory and learning phase (face-to-face) Installation and testing of app, explanation of intervention, conduction of al mindfulness exercises in the presence of study investigator From now on: Individual daily meditation + daily EMA data collection Possibility of consulting the study coordinator in person and if necessary discussing/solving problems in period 1
	Intermediate (4 weeks):
	 Paper-pencil data collection (+ hospitalization and exacerbation rate) Psychophysiological data collection
	Exit (8 weeks):
	 Paper-pencil data collection (+ hospitalization rate, exacerbation rate credibility/expectancy) Psychophysiological data collection Short exit-interview (telephone)

	Period 2 (follow-up)
	Follow-up 1 (4 months):
	 Paper-pencil data collection (+ hospitalization and exacerbation rate) Psychophysiological data collection Chronic stress (collection of hair sample)
	Follow-up 2 (6 months):
	 Paper-pencil data collection (+ hospitalization and exacerbation rate) Psychophysiological data collection Chronic stress (collection of hair sample) Post-monitoring interview
INTERVENTION	Daily short mindfulness exercises delivered via app
	 App provides 4 audio-files of guided mindfulness exercises Length: 10-15 minutes Mindfulness exercises: Body awareness meditation (Body-scan) Sitting meditation: awareness of the heartbeat Sitting meditation: awareness of the body Sitting meditation: awareness of sounds
	Dose: Patients can choose individually between exercises
	Daily practice: instructions to practice at least once each day, either in the morning or the evening (patients choose in the beginning if they prefer meditating in the morning or in the evening)
	Additional practice: additional meditations are possible and encouraged (it is advised to practice when experiencing respiratory problems, feeling distressed, feeling stressed or whenever considered to be beneficial)
CONTROL	Waitlist control group (receiving treatment as usual during the intervention period)
CONDITION	(same collection of psychophysiological, psychological and biological data, except for the intervention-related measures right before and after the intervention)
INCENTIVES	Weekly "checking-in calls"
CONCOMITANT MEDICATION	Allowed (but must be monitored)
PRIMARY	Feasibility (exit interview, drop-out-rate)
OUTCOME VARIABLES	Intermediate and long-term effects of daily mindfulness practice:
VANIADLES	• Psychological distress (Hospital Anxiety and Depression Scale)
SECONDARY OUTCOME	 Immediate effects of mindfulness exercises: Acute perceived stress (visual analogue scale)
VARIABLES	Dyspnea (Borg Dyspnea Scale) Delayation (Likert and a MDRE)
	 Relaxation (Likert scale based on MDBF) Affect (anxiety, depression, happiness; based on HADS) Overgen seturation in blood (Bules Ovimeter)
	Oxygen saturation in blood (Pulse Oximeter)

	Intermediate and long-term effects of daily mindfulness practice:
	 Heart rate variability, heart rate (chest belt) Electrodermal activity (EDA-sensors) Chronic stress (hair-cortisol) Chronic stress (Perceived Stress Scale) Health related quality of life (Chronic Respiratory Questionnaire) Health status impairment (COPD-Assessment Test) Fatigue (Multidimensional Fatigue Inventory) Mindfulness (German Version of Freiburg Mindfulness Inventory – Freiburger Fragebogen zur Achtsamkeit) Self-compassion (Self Compassion Scale) Breathlessness Catastrophizing (Breathlessness Catastrophizing Scale) Further outcomes: Compliance regarding medication Perception of exacerbations (exit interview)
	Hospitalization rateFrequency and intensity of exacerbations
STATISTICAL METHODOLOGY	Primary hypotheses: It is hypothesized that the digital MBI will be feasible in the ambulant setting. Furthermore, it is assumed that the digital intervention will reduce psychological
	distress. The feasibility of the study will be examined using descriptive analyses, looking deeper into drop-out-rates, recruitment, adherence and patients' personal factors.
	Statistical analyses:
	Groups (intervention vs. waitlist) will be compared regarding subjective variables (e.g. psychological distress), biological variables (hair cortisol levels), and physiological responses of the autonomous nervous system (heart rate variability, electrodermal activity) to the mental stressor using analyses of variance (ANOVAs) with repeated measurement. These analyses test for main effects of time (within subject factor) and group (between subject factor) as well as their interaction effect. In case the requirements of ANOVAs are not met, a non-parametric pendant will be used. Furthermore, mediating (e.g. mindfulness) and moderating (e.g. age, gender, disease severity) effects will be analysed.
	For the analysis of the EMA data in the intervention group, multilevel modelling will be used to fit the nested data structure. A two-level model (level 1 = within persons, level 2 = between persons) will be used, with all the assessed subjective variables (e.g. momentary stress) nested on level 1 due to multiple measurements. Pre-post effects of the assessed subjective variables will examine the immediate effects of the MBI.
	Telephone exit interviews will be recorded and analysed using thematic analysis and a mixed methods approach.
DATA	Paper-pencil-data:
MANAGEMENT	• Digitalization: As data are collected on different sites by student research assistants, data will firstly be transported to the Department of Clinical and Health Psychology, University of Vienna, Austria. There, data will be digitalized.

For this process, data will be safely stored in a locked cupboard in the Department of Clinical and Health Psychology, University of Vienna, Austria. Only members of the research team have access to the key.

Klinik Floridsdort

- Final storage of physical data: The study coordinator will transport the physical data safely to the Klinik Ottakring, Vienna, Austria, where the data is finally stored in a locked cupboard. Only members of the research team have access to the key.
- Storage of digital data: Digital data will be stored on the share server of the research team led by [name] [name] (University of Vienna, Austria). A project folder "39 SPIROMIND" was created for the data storage. Each person's access to the folder must be approved by [name] [name] and must be activated by the department's IT team. Only members of the SPIROMIND research team have access to the folder. Additionally, data will be stored on the study coordinator's server of the Klinik Ottakring, Vienna, Austria, and on the study coordinator's server of the Department of Clinical and Health Psychology, University of Vienna, Austria.
- Analysis: Data will be analysed using the software IBM SPSS Statistics, version 24, and the software R, version 3.4.2.

EMA data:

- Access to data: Data are stored on the study's private account of the software MovisensXS. Only members of the research team have access to the account.
- Storage of data: Data will be exported from MovisensXS and stored on the share server of the research team led by [name] [name] (University of Vienna, Austria). A project folder "39 SPIROMIND" was created for the data storage. Each person's access to the folder must be approved by [name] [name] and must be activated by the department's IT team. Only members of the SPIROMIND research team have access to the folder. Additionally, data will be stored on the study coordinator's server of the Klinik Ottakring, Vienna, Austria, and on the study coordinator's server of the Department of Clinical and Health Psychology, University of Vienna, Austria.
- **Analysis:** Data will be analysed using the software IBM SPSS Statistics, version 24, the software R, version 3.4.2, and HLM.

Physiological data:

- Access to data: Data will be exported from the devices using the Movisens Data Manager. This will be conducted by the student research assistants.
- Storage of data: Data will then be stored on the share server of the research team led by [name] [name] (University of Vienna, Austria). A project folder "39 SPIROMIND" was created for the data storage. Each person's access to the folder must be approved by [name] [name] and must be activated by the department's IT team. Only members of the SPIROMIND research team have access to the folder. Additionally, data will be stored on the study coordinator's server of the Klinik Ottakring, Vienna, Austria, and on the study coordinator's server of the Department of Clinical and Health Psychology, University of Vienna, Austria.
- Analysis: Data will be analysed using the software Movisens Data Analyser (Base + Cardio/HRV), IBM SPSS Statistics, version 24, and the software R, version 3.4.2.

Biometric data (hair samples):

• **Collection:** As data are collected on different sites by student research assistants, data will firstly be transported to the Department of Clinical and

Klinik Ottakring

Health Psychology, University of Vienna, Austria. There, data will be safely stored in a locked cupboard in the Department of Clinical and Health Psychology, University of Vienna, Austria, until data will be analysed. Only members of the research team have access to the key. Biometric analysis: A member of the research team will safely transport the data to the biochemical laboratory of the Faculty of Psychology, Vienna, Austria, where the data will be analysed by researchers unrelated to the SPIROMIND study. The biochemical laboratory ensures safe storage of the data. Final storage of biometric data: The study coordinator will transport the biometric data safely to the Klink Ottakring, Vienna, Austria, where the data is finally stored in a locked cupboard. Only members of the research team have access to the key. Storage of digital data: Digital data will be stored on the share server of the research team led by [name] [name] (University of Vienna, Austria). A project folder "39 SPIROMIND" was created for the data storage. Each person's access to the folder must be approved by [name] [name] and must be activated by the department's IT team. Only members of the SPIROMIND research team have access to the folder. Additionally, data will be stored on the study coordinator's server of the Klinik Ottakring, Vienna, Austria, and on the study coordinator's server of the Department of Clinical and Health Psychology, University of Vienna, Austria. **Analysis:** Digital data will be analysed using the software IBM SPSS Statistics, version 24, and the software R, version 3.4.2. Qualitative data: **Collection:** Data will be collected using a recorder. Storage: Data (audio-files) will be stored on the share server of the research team led by [name] [name] (University of Vienna, Austria). A project folder "39 SPIROMIND" was created for the data storage. Each person's access to the folder must be approved by [name] [name] and must be activated by the department's IT team. Only members of the SPIROMIND research team have access to the folder. Additionally, data will be stored on the study coordinator's server of the Klinik Ottakring, Vienna, Austria, and on the study coordinator's server of the Department of Clinical and Health Psychology, University of Vienna, Austria. Analysis: Data will be analysed using the softwares f4transcript and f4analyse.

Klinik Floridsdorf

akultät für Psycholo

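### The secondary question on subjective state and oxygen saturation under the Stroop test has no measurement scheduled at the Stroop test

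*Protocol*

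**What the plan says.** Under OBJECTIVES, the Protocol has two secondary questions about the Stroop test. One concerns stress level and reactivity and names heart rate variability and electrodermal activity. The next concerns how patients deal with the stressor and asks: "Are there effects on anxiety, panic, acute perceived stress, relaxation, affect and oxygen saturation".

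The measures attached to the Stroop test are these:

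- Executive Summary, Methods: "Physiological measures will be assessed during the conduction of a cognitive stress test (Stroop-test), as well as before and after the conduction (at rest". The sentence before it defines the physiological measures as heart rate variability, electrodermal activity and heart rate.
- MEASUREMENTS, psychophysiological data: "heart rate variability, electrodermal activity (before, during and after the conduction of a cognitive task (Stroop-test".
- STATISTICAL METHODOLOGY: the responses to the mental stressor are again heart rate variability and electrodermal activity.

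The momentary ratings and oximetry appear elsewhere:

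- MEASUREMENTS sets them out as "EMA data collection (daily for intervention period of 8 weeks", with "pre-meditation (event-based): dyspnea, acute perceived stress, relaxation anxiety, depression, happiness, oxygen saturation (pulse oximeter" and the same list after meditation.
- STUDY TIME-LINE starts them on Day 1: "From now on: Individual daily meditation + daily EMA data collection". The baseline psychophysiological session is on Day 0.
- SECONDARY OUTCOME VARIABLES lists them under one heading only: "Immediate effects of mindfulness exercises: Acute perceived stress (visual analogue scale", followed by the other acute items.
- CONTROL CONDITION gives the waitlist arm the "same collection of psychophysiological, psychological and biological data, except for the intervention-related measures right before and after the intervention".

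**The concern.** The question is about the effect of daily practice on the reaction to a stressor. To answer it, the same ratings must be taken close to the stressor in both arms, with a baseline. The Protocol names the constructs but appears to schedule them only around a different event, meditation, which the waitlist arm does not undergo during the comparison period.

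If the sites follow the schedule as written, the Stroop sessions will yield autonomic data and nothing on how patients felt or on oxygen saturation. This cannot be repaired at the analysis stage. The Day 0 baseline in particular is lost once a patient has passed it.

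**Working it through.** The Protocol gives no figure to reproduce here. The check is to follow each named item from the question through the measurement, outcome and control-arm entries.

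| Item in the question | Scheduled at the Stroop test? | Where it is scheduled |
|---|---|---|
| Anxiety | No | Momentary item around meditation; also the HADS in the paper questionnaires |
| Panic | No | No instrument named |
| Acute perceived stress | No | Momentary item around meditation |
| Relaxation | No | Momentary item around meditation |
| Affect | No | Momentary items (anxiety, depression, happiness) around meditation |
| Oxygen saturation | No | Pulse oximeter around meditation |

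The result is 0 of 6. The outcome list counts anxiety as part of affect. If the two are merged, the result is 0 of 5.

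**Could the meditation-linked ratings stand in?** The Stroop sessions take place at baseline (Day 0), 4 weeks, 8 weeks, 4 months and 6 months: 5 visits × 2 arms = 10 arm-visits. The momentary ratings run from Day 1 to 8 weeks in the intervention arm only.

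- Intervention arm: the rating period covers the 4- and 8-week visits (counting the 8-week exit as inside it), so 2 of 5.
- Waitlist arm: 0 of 5.
- Baseline, both arms: 0 of 2.
- Total: 2 of 10.

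Even at those 2 arm-visits, what triggers a rating is a meditation at home, not the Stroop test. The overlap in time therefore gives no Stroop-linked data, and no between-arm comparison is possible at any visit.

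**Could the visit questionnaires stand in?** The HADS and the Perceived Stress Scale are collected in both arms at the same five time points. They belong to the general paper battery, are not placed before or after the Stroop test, and do not cover relaxation or oxygen saturation. The Protocol itself separates acute perceived stress (this question) from perceived stress (the next question).

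**Contrast with the neighbouring question.** Heart rate variability and electrodermal activity carry through from the reactivity question to MEASUREMENTS, outcomes and analysis. The six items here carry through to none of these as Stroop measures.

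**The case against.** The strongest reply is that the ratings may be planned and simply not written down. The synopsis lists are plainly incomplete. MEASUREMENTS omits heart rate and hair cortisol, both of which are planned elsewhere. The 8-week entry in STUDY TIME-LINE omits the hair sample that the Executive Summary schedules. Medication compliance is an outcome with no entry in either place. The list in the question is also not a copy of the list for the exercises: it drops dyspnea and adds panic, which suggests a list made for the Stroop test. This much stands: the Protocol shows that the measures are not scheduled, not that nobody intends to take them. But heart rate and hair cortisol are scheduled somewhere in the document, whereas no entry places any of these six items at the Stroop test.

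A second reply is that the waitlist exemption covers only measures around the intervention, so Stroop ratings, if they existed, would be required in both arms. That reading is fair. It helps only once such ratings are in the schedule.

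Third, the count of arm-visits says little, because the momentary ratings are a home diary and not a visit measure. That is also fair. The count serves only to show that the diary cannot substitute, and the finding does not depend on it.

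Finally, this is a 30-patient pilot, one secondary question is affected, and the autonomic Stroop question is properly scheduled. That limits the importance of the point but does not remove it. What is measured, when and in which arm is for the protocol to fix; a statistical analysis plan cannot create data that were not collected.

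**Conclusion.** The point holds. None of the 6 named items (5 if anxiety is counted within affect) has a measurement before, during or after the Stroop test, and panic has no named instrument. As written, the arms cannot be compared on their subjective or oxygen-saturation reaction to the stressor, and the missing data could not be recovered.

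This rests on the text of the Protocol alone, whose entries on this point are legible and agree with one another. It assumes that sites collect what the Protocol lists and no more. If unlisted Stroop ratings are in fact planned, the fault is one of documentation and easily mended. The consequence is limited to one secondary question; the primary outcomes and the autonomic Stroop question are unaffected. The change should be made, but the trial's main purpose does not depend on it.

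**What to change.** Reconcile the question under OBJECTIVES with MEASUREMENTS, STUDY TIME-LINE and SECONDARY OUTCOME VARIABLES in one of two ways.

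1. **Schedule the measures.** Take the existing momentary items (acute stress, relaxation, anxiety, depression, happiness) and one oximeter reading just before and just after the Stroop test, at all five visits, in both arms. Add a panic item or drop panic from the question. List these as outcomes separate from the immediate effects of the exercises. If the ratings are already planned, this means only writing them into those entries.
2. **Delete the question.**

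Burden of option 1, per patient:

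- Ratings without panic: 5 items × 2 occasions × 5 visits = 50, or 10 per visit.
- Ratings with a panic item: 6 × 2 × 5 = 60, or 12 per visit.
- Oximeter readings: 2 × 5 = 10, or 2 per visit.

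The psychophysiological sessions already take place in both arms at all five time points, so no visit is added. The short items and access to an oximeter must be available at the waitlist sessions too, which the Protocol does not now provide for; an oximeter kept for the sessions would do. Option 2 costs one deleted line and gives up the question.
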